# 1.0 Objectives

1.1 Purpose: This will be a single site, 24-week double-blind, randomized, placebocontrolled pilot and feasibility clinical trial designed to estimate the treatment effect and tolerability of lisdexamfetamine (Vyvanse™) for the treatment of severe obesity in children ages 6 to < 12 years. After careful screening, all eligible participants (n=44) will be randomized, 1:1, to either lisdexamfetamine plus lifestyle therapy or placebo plus lifestyle therapy for 24 weeks of intervention. Participants and their parent/guardian will attend 8 in-person and 6 virtual visits. Participants will undergo regular assessments of anthropometrics, blood pressure, heart rate, and side effects and interval assessments of body composition, bone age, Tanner stage, laboratory tests, and questionnaires.

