# A.5. Tolerability of LDX for the treatment of severe obesity in children is unknown

Although psychostimulants, including LDX, have a long-standing, well-established safety profile,  the relative tolerability of these medications in children who do not have ADHD has yet to be established. Aside from decreased appetite, the most common side effects of psychostimulants in children with ADHD include insomnia, upper abdominal pain, and irritability. Particularly relevant to patients with obesity are the impact of psychostimulants on blood pressure, heart rate and linear growth, the effects of which tend to be dose dependent in children with ADHD.  Clinical trials of LDX for the treatment of ADHD in children report

PROTOCOL TITLE: Lisdexamfetamine for the Treatment of Severe Obesity in Children Aged

6 to 12 Years

VERSION DATE: 19Sep2025

[figure not shown]
mean increases in systolic blood pressure of 2-4 mm Hg and in heart rate of 3-7 bpm. The clinical significance of this effect on the cardiovascular system is uncertain, especially for children with obesity who may be at higher risk of having underlying cardiovascular impairment such as hypertension. Importantly, in adults with obesity treated with phentermine, also a noradrenergic agent, blood pressure tends to decrease as a function of weight loss. 12 Thus, measuring the impact of LDX on blood pressure and heart rate in children with obesity is critical for assessing its utility as an adjunct treatment for obesity in this population. Regarding linear growth, psychostimulants have been shown to have adverse effects on height velocity at various stages of childhood, including prepuberty. 13,14 However, final adult height does not appear to be impacted. 15 Similarly, obesity can effect growth and has been associated with taller stature during childhood but decreased growth velocity in adolescence; the net result again is no association between childhood weight status and adult height. 16 That said, as both psychostimulant use and obesity can affect growth velocities during the pre- and peri-pubertal periods, the net effect of both of these simultaneously during this stage of development is unclear and warrants further investigation.

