#### 14.0 Statistical Considerations

Data Analysis Plan: Descriptive analyses of baseline characteristics and outcomes will include means and standard deviations, median and range for continuous variables and frequencies with percentages for categorical variables. Safety analyses (including Barkley's Side Effect Rating Scale and incidence of hypertension and tachycardia) will be primarily descriptive reporting the number and percentage of adverse events during participation in the study. All safety outcomes will be evaluated and monitored throughout the study. Confidence intervals (Cis) and P-values for all analyses will be based on robust variance estimation. Statistical significance will be considered as p<0.05.

PROTOCOL TITLE: Lisdexamfetamine for the Treatment of Severe Obesity in Children Aged

6 to 12 Years

VERSION DATE: 19Sep2025

**Aim 1:** Estimate the treatment effect of LDX plus lifestyle therapy vs placebo plus lifestyle therapy on changes in BMI (%BMIp95 primary endpoint), body fat, cardiometabolic health and quality of life (QOL) from baseline to 24 weeks. **H1:** We hypothesize that LDX compared to placebo will result in a greater mean decrease in %BMIp95 and body fat, and improved cardiometabolic health and QOL at 24 weeks.

The primary outcome measurement will be absolute change in percent of the BMI 95th percentile abbreviated %BMIp95. Although we will report on other metrics of BMI change including absolute BMI change and percent BMI change, we chose %BMIp95 as the primary outcome measurement because of its clinical utility in measuring changes in BMI in young children who have severe obesity and a consensus in the research community that expressing BMI change relative to the 95th percentile is preferred over other metrics such as BMI standard deviation score a.k.a. z-score. The limitation of BMIz is explained by the flattening of BMIz curve at values significantly above the 95th percentile, despite the wide variance of BMIs in youth with severe obesity, which therefore leads to an underestimation of clinically significant improvement in weight status). The primary outcome will be the mean change in %BMIp95 from baseline to 24 weeks follow-up compared between treatment groups, while adjusting for baseline value for added precision. See Table 1 for examples of changes in BMI and corresponding changes in %BMIp95.

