| Table 1. Exa           | imples of chan             | ges in BMI and co                   | rresponding o            | changes in %BMIp                    | 95                                   |                                  |
|------------------------|----------------------------|-------------------------------------|--------------------------|-------------------------------------|--------------------------------------|----------------------------------|
| Example
Participant | Starting
BMI
(kg/m²) | Starting
%BMIp95                 | Ending
BMI
(kg/m2) | Ending
%BMIp95                   | Absolute
change in
BMI (kg/m2) | Absolute
change in
%BMIp95 |
| 6 yo girl              | 26.37                      | 140% of 95 th percentile | 25.2                     | 134% of 95 th percentile | -1.17                                | -6 percentage points             |
| 10 yo boy              | 39.8                       | 135% of 95 th percentile | 28.7                     | 130% of 95 th percentile | -1.1                                 | -5 percentage points             |

Power Analysis: Given this is a pilot and feasibility study, the sample size is not driven by a power analysis stemming from a formal statistical evaluation of a hypothesis test associated with the primary endpoint the trial. Instead, the objectives of this study revolve around identifying key information on execution of the study and experience of participants to best inform the design of a subsequent, larger study to examine efficacy and effectiveness.

Secondary endpoints for Aim 1 are also continuous and will be evaluated in a similar fashion, with adjustment for baseline value. These include percent body fat, lab measurements of glucose, insulin, lipids (total-, LDL-, HDL-cholesterol, and

PROTOCOL TITLE: Lisdexamfetamine for the Treatment of Severe Obesity in Children Aged

6 to 12 Years

VERSION DATE: 19Sep2025

triglycerides), hemoglobin A1c, ALT, AST, and PedsQL. We will also report on other metrics of BMI change, including absolute BMI change and percent BMI change.

**Aim 2:** Generate estimates of the tolerability and safety of LDX used for the treatment of severe obesity in children.

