**H2:** We hypothesize that at least 80% of participants will tolerate an LDX dose of ≥30 mg daily (recommended starting dose) for 24 weeks and that the LDX group compared to the placebo group will not demonstrate clinically significant increases in blood pressure or heart rate.

We will define feasibility to conduct the larger trial if, in this pilot study, >80% of participants randomized to LDX tolerate a dose of >30 mg daily, the recommended starting dose, for 24 weeks and there are no statistically significant differences between the LDX group and placebo group in incidence of developing stage 1 hypertension or tachycardia. Outcomes will be captured for all regardless of tolerability and will inform inclusions/exclusion criteria and dose escalation schedule for the subsequent trial. Safety outcomes will be monitored carefully and include instances of stage 1 hypertension (defined as SBP and/or DBP ≥95th percentile on 3 separate occasions) and confirmed by 24 hour ambulatory blood pressure monitor) and tachycardia (defined as heart rate ≥120 bpm at rest measured on 3 separate occasions). The Barkley Side Effect Rating Scale will also be measured at every 2 weeks during dose escalation and then every 4 weeks for the remainder of the study and will be used to help identify reasons for limited tolerability should this occur. Height velocity in cm/year will be determined by the difference in measured height between the baseline and 24-week assessments and will be used to calculate a height velocity SDS (z-score). Given the potential for LDX to disrupt sleep and the impact of sleep on obesity, participant sleep will be measured objectively using accelerometry with the ActiGraph (GT3X-BT) device, which has been shown to have acceptable reliability and validity in sleep-wake detection compared with laboratory-based polysomnography. Nighttime sleep efficiency, defined as the portion of time dedicated to sleep that is spent asleep, will be evaluated as the primary sleep endpoint of interest, with higher scores representing more efficient sleep. All indexes will be calculated using the ActiLife software. Participant mental health will be monitored by the Columbia-Suicide Severity Rating Scale (C-SSRS) and Children's Depressive Inventory-2 (CDI-2).

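### The feasibility rule takes a non-significant difference in hypertension or tachycardia at 22 children per arm as acceptable, with no named test, effect measure or confidence limit, and no adjusted blood-pressure or heart-rate contrast beside it

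*Combined protocol and SAP*

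**What the plan says.** Section 14.0, Aim 2, gives two conditions for calling the larger trial feasible. One is a tolerability proportion in the LDX arm. The other is "no statistically significant differences between the LDX group and placebo group in incidence of developing stage 1 hypertension or tachycardia". The related hypothesis, H2, is worded differently: the "LDX group compared to the placebo group will not demonstrate clinically significant increases in blood pressure or heart rate".

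The statistical text that bears on the second condition is general:

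- Section 1.0: "all eligible participants (n=44) will be randomized, 1:1", so 22 per arm.
- Section 14.0, Data Analysis Plan: "Statistical significance will be considered as p<0.05" and "P-values for all analyses will be based on robust variance estimation". Safety analyses are described there as mainly descriptive, with "means and standard deviations, median and range for continuous variables".
- Section 14.0, Power Analysis: "the sample size is not driven by a power analysis".

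Sections 4.2 and 14.0 define the events for an individual child: blood pressure at a 95th-percentile threshold on three occasions with ambulatory confirmation, and a resting heart rate at a 120 bpm threshold on three occasions. Section 2.0, on the tolerability of LDX, reports "mean increases in systolic blood pressure of 2-4 mm Hg and in heart rate of 3-7 bpm" from trials in children with ADHD. It calls the clinical significance uncertain and regards measuring this impact in children with obesity as critical. The schedule of events collects blood pressure and heart rate at every in-person visit.

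**The concern.** A significance test in a small sample answers whether the data rule out no difference. It does not answer whether the data rule out a difference that matters. Used as a go condition it works the wrong way round: the fewer the children and the rarer the events, the easier it is to pass. No test, effect measure or confidence limit is attached to the incidence comparison. Robust variance is a way of computing standard errors and names none of these.

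The second part is an omission. Section 14.0 gives percent body fat, laboratory values, quality of life and the exploratory measures a baseline-adjusted arm contrast. It names none for systolic pressure, diastolic pressure or heart rate. The Aim 1 list may not be exhaustive, and crude arm means would come out of the descriptive summaries. Still, the comparison that bears most directly on H2 is not specified.

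At stake is the safety conclusion carried into the larger trial.

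**Working it through.** The plan gives no power, rate, margin or SD for this comparison, so there is no figure of its own to reproduce.

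**Inputs.** From the documents: 22 per arm, alpha 0.05. Assumed: two-sided testing, all event rates, SDs, correlations and evaluable numbers.

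**Step 1. Counts, with no assumed rates: 3/22 LDX against 0/22 placebo.**

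- Fisher: 2 × C(22,3)/C(44,3) = 2 × 1540/13244 = 0.233.
- Pearson: pooled rate 3/44 = 0.0682; SE = √(0.0682 × 0.9318 × 2/22) = 0.0760; z = 0.1364/0.0760 = 1.79; p = 0.073.
- Unpooled Wald on the risk difference: SE = √(0.1364 × 0.8636/22) = 0.0732; z = 1.86; p = 0.062.
- Likelihood ratio: 2 × [3 ln(3/22) + 19 ln(19/22) − 3 ln(3/44) − 41 ln(41/44)] = 2 × (−8.763 + 10.952) = 4.38 on 1 df; p = 0.036.
- Newcombe score interval: Wilson limits are 4.7% to 33.3% for 3/22 and 0% to 14.9% for 0/22. Lower limit = 0.136 − √((0.136 − 0.047)² + 0.149²) = −0.037; upper limit = 0.136 + (0.333 − 0.136) = 0.333.

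Three tests pass the condition and one fails it, on the same data. A robust Wald test on a log or logit scale cannot be computed with a zero cell.

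| LDX v placebo events | Fisher | Pearson | Wald | 95% score interval (points) |
|---|---|---|---|---|
| 3 v 0 | 0.233 | 0.073 | 0.062 | −3.7 to +33.3 |
| 4 v 0 | 0.108 | 0.036 | 0.027 | −0.2 to +38.5 |
| 5 v 1 | 0.185 | 0.079 | 0.068 | −3.2 to +39.2 |

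At 4 v 0, Fisher passes and Wald fails.

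**Step 2. Chance that a true excess is flagged.** Binomial probabilities were summed over all tables with p<0.05. The range runs from Fisher to unpooled Wald. For either of two endpoints, assumed independent and equally raised, the chance is 1 − (1 − p)².

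| Assumed LDX v placebo rate | One endpoint | Either of two |
|---|---|---|
| 10% v 0% | 6-17% | 12-31% |
| 15% v 5% | 9-18% | 17-33% |
| 20% v 5% | 20-33% | 36-55% |
| 20% v 0% | 46-67% | 71-89% |

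If only 18 per arm were evaluable, 20% v 5% would be flagged 13-26% of the time for one endpoint.

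**Step 3. What an adjusted mean contrast would give.** For the mean of k post-baseline visits adjusted for baseline, with correlation r between any two visits, half-width = t(2n−3) × SD × √((1 + (k−1)r)/k − r²) × √(2/n). For Week 12-24, k = 4; n = 22; t(41) = 2.020.

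- Systolic, SD 8 mm Hg, r = 0.7: 2.020 × 8 × √0.285 × 0.3015 = 2.6. SD 12, r = 0.5: 2.020 × 12 × √0.375 × 0.3015 = 4.5.
- Heart rate, SD 10 bpm, r = 0.7: 3.3. SD 15, r = 0.5: 5.6.

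With 18 per arm these become 2.9-5.0 mm Hg and 3.6-6.2 bpm.

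**The case against.** The strongest reply is that this is a pilot. The plan disclaims a power-based sample size, keeps safety analysis mainly descriptive, and nowhere says that passing the condition shows absence of harm. The condition can only add a brake beside the tolerability hurdle. This stands in part: lack of power is no fault here, and a reader who infers that the plan claims LDX safe on p≥0.05 goes beyond the text. What does not follow is that a significance test is a sound brake.

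A reader might also infer that H2 is left with no means of being answered. The documents do not support that. The definitions in sections 4.2 and 14.0 are measured by blood pressure and heart rate, and can fairly be read as putting part of H2 into operation. What is missing is the arm-level mean contrast with its interval and a stated size for a clinically significant increase.

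A third tempting reading is that 3 v 0 would pass whichever test is used, or that the rule almost never flags harm. The likelihood-ratio result contradicts the first. The second fails for a large excess over a near-zero placebo rate, which is flagged more often than not under most of the assumptions shown.

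Finally, the rises of 2-4 mm Hg and 3-7 bpm in section 2.0 come from ADHD trials. They are not stated there as differences from placebo, nor as the effect expected here. In the same place the protocol notes that blood pressure tends to fall with weight loss in adults on phentermine.

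**Conclusion.** The concern holds as a weakness in a stated decision rule and should be fixed. With 22 per arm, passing the incidence condition is compatible with an excess of about 33 points at 3 v 0 (under three of the four tests) and about 39 points at 5 v 1. At 3 v 0 and 4 v 0 the choice of test alone decides pass or fail. Those counts and intervals need no assumed rates. The 6-18% chance of flagging a 10-point excess in one endpoint (12-33% for either of two) does rest on assumed rates, and on independence for the second range.

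The omission of a baseline-adjusted contrast for blood pressure and heart rate is real but partial, given the individual event definitions. Protection of children during the trial (sections 12.1 and 17.2) and the tolerability condition are separate matters and are not criticised.

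**What to change.** 1. Replace the non-significance condition; do not simply delete it, since feasibility would then rest on tolerability alone. Report the incidence of each event by arm with exact 95% CIs, and the arm difference with a score-type 95% CI. Base the safety part of the go decision on that estimate and interval, together with the contrast in item 2, against limits that the investigators set before unblinding. State that p≥0.05 will not be read as absence of harm.
2. Pre-specify, in all randomised children, the baseline-adjusted LDX-minus-placebo difference in systolic pressure, diastolic pressure and heart rate over the in-person visits, with 95% CIs. Say whether the estimate or the upper limit is judged. Both items are needed: section 12.1 lowers the dose when hypertension is confirmed, which can dilute the mean difference, while incidence still counts those children.

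The cost is wording plus one analysis of data already collected. The downside is a less reassuring statement. Even 0 v 0 events leaves −14.9 to +14.9 points, and the exact upper limit for 0/22 is 1 − 0.025^(1/22) = 15.4%. If the upper limit decides, the threshold must be chosen with its width in view. Assuming that the true arm difference equalled the ADHD-trial increases, the average upper limit for the Week 12-24 mean would be 2 + 2.6 = 4.6 to 4 + 4.5 = 8.5 mm Hg, and 3 + 3.3 = 6.3 to 7 + 5.6 = 12.6 bpm.

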#### 3.3 Description:

LDX: LDX, a psychostimulant prodrug of dextroamphetamine, is FDA-approved for ADHD in children ≥6 years of age and for binge eating disorder in adults. It is available in capsules of 10, 20, 30, 40, 50, 60, and 70 mg. It is orally administered once daily and has a half-life of 12 hours. After a single dose, the pharmacokinetics are linear between 30 and 70 mg in children ages 6-12 years, and both the clinical efficacy for ADHD symptoms and weight loss side effects are dose dependent. Following single doses of 30 mg to 70 mg, the weight/dose normalized area under the curve and maximal concentration values are the same in 6-12 year olds compared to adults. Per the package insert, the recommended starting dose for children ≥6 years of age with ADHD is 30 mg daily. The dose is adjusted by 10 or 20 mg increments at weekly intervals up to a maximum of 70 mg daily. The target dose is one that balances the clinical efficacy with tolerability. For binge eating disorder in adults, the recommended dose is 50-70 mg daily. To operate conservatively and allow for maximum tolerability, we will start at 30 mg daily for 2 weeks, then 40 mg daily for 2 weeks, then 50 mg daily for 2 weeks, then 60 mg daily for 2 weeks, then 70 mg daily for the remaining 14 weeks. We will not use a forced titration schedule. That is, for patients who do not tolerate the full dose escalation schedule, we will maintain the dose at the maximum tolerated dose for the remainder of the trial. Also, we will not escalate the dose after week 10, which is the end of the planned dose escalation schedule. A participant's dose may be decreased for medication intolerance anytime during the trial; the dose will be reduced by 10 mg at weekly intervals until a tolerable dose is achieved. If a participant cannot tolerate the smallest dose, 10 mg, then drug/placebo will be discontinued but the participant will remain in the trial. This flexible dosing will allow for maximal time on medication. Placebo capsules that are identical in appearance to the LDX capsules will be made by the University of Minnesota Investigational Drug Service Pharmacy, which will manage all trial product.

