- Tolerability and Safety Outcomes. The feasibility of conducting the larger clinical trial will depend on whether or not participants can tolerate LDX at doses that are effective for inducing BMI reduction. We will define tolerability as being able to tolerate a dose of at least 30 mg daily (the recommended starting dose) for the duration of the study. Importantly we will also measure outcomes of children taking doses less than 30 mg daily (i.e., 20 mg or 10 mg) as this information will be important for informing the dosing of the larger, definitive trial. We anticipate that participants taking LDX will have side effects at the same rate as patients who take LDX for the treatment of ADHD, so we will not define tolerability as not having any side effects whatsoever. Rather, the parent/guardian and participant will subjectively decide if the side effects, if present, are severe enough to warrant discontinuation of the study medication or reducing the dose below 30 mg daily. From an objective standpoint, every two weeks during dose escalation and every 4 weeks for the remainder of the study we will administer the Barkley's Side Effect Rating Scale which was developed specifically to monitor side effects from psychostimulants. This questionnaire, completed by the parent/guardian (and sometimes with the child's help) requests feedback on 17 items on a 9-point Likert scale including typical physical side effects (e.g., decrease appetite, insomnia, stomachaches, and headaches) and behavioral symptoms (e.g., irritability, anxiety).78. Other measures of tolerability will include incidence of developing stage 1 hypertension and tachycardia, measured by blood pressure and heart rate. Stage 1 hypertension is defined as SBP and/or DBP >95th percentile on three separate occasions and will be confirmed by a 24hour ambulatory blood pressure monitor. Tachycardia in childhood is defined as heart rate > 120 bpm at rest measured on three separate occasions.80

PROTOCOL TITLE: Lisdexamfetamine for the Treatment of Severe Obesity in Children Aged

6 to 12 Years

VERSION DATE: 19Sep2025

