# 12.0 Risks to Participants

#### 12.1 Foreseeable Risks:

Risks of blood sampling: There is a minimal risk of bruising, fainting and infection associated with blood draws.

Risks of exposure to ionizing radiation: The DXA scans and the bone age scans involve exposure to a very low dose of ionizing radiation. The average amount of radiation that the average person would receive from the bone age scan and DXA scans used in this study is less than 2% (3 mrem) of that received from natural sources of radiation by a Minnesota resident in one year (300 mrem).

Risks of Lisdexamfetamine: Adverse reactions occurring in ≥5% and at a rate at least twice that of placebo in children include anxiety, dry mouth, diarrhea, nausea, vomiting, upper abdominal pain, irritability, insomnia and dizziness. Rarely reported adverse events include hypertension and tachycardia. Additionally, suppression of linear growth is a known class effect, though final adult height is not impacted.

Although not recommended as a routine practice, baseline ECG will be obtained on all participants to screen for underlying arrhythmia. If SBP and/or DBP is ≥95th percentile or ≥130/80 (whichever is lower), blood pressure will be measured again on a separate visit within 2 weeks. If BP remains elevated on 3 separate visits, the participant will undergo a 24 hour ambulatory blood pressure monitor (ABPM) to confirm or rule out a diagnosis of hypertension.

If elevated BP emerges and is confirmed on 2 additional occasions during lisdexamfetamine dose escalation, further dose escalation will halt until the results of a 24 hour ABPM are available.

If hypertension is confirmed, lisdexamfetamine dose will be reduced until blood pressure normalizes.

- If SBP and/or DBP is ≥95th percentile+12 mmHg or ≥140/90 (whichever is lower) and the participant is symptomatic, lisdexamfetamine will be discontinued and the participant will be referred to emergent care.
- If heart rate is ≥140 bpm, an EKG will be obtained and the participant will be assessed for the need for emergent or non-emergent medical intervention, including the need to reduce or discontinue lisdexamfetamine dose.

*Risks of indirect calorimetry*: Potential risks include feeling claustrophobic from the mask/hood.

PROTOCOL TITLE: Lisdexamfetamine for the Treatment of Severe Obesity in Children Aged 6 to 12 Years

VERSION DATE: 19Sep2025

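### A child whose dose is lowered for a fast heart rate can count as both free of tachycardia and tolerating the drug, which tilts the Aim 2 feasibility rule towards proceeding

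*Combined protocol and SAP*

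**What the plan says.** **Outcome.** Section 14.0, Aim 2, defines "tachycardia (defined as heart rate ≥120 bpm at rest measured on 3 separate occasions". Stage 1 hypertension also needs three occasions, and then confirmation by 24-hour ambulatory monitoring. Section 4.2 treats both as tolerability outcomes: "Other measures of tolerability will include incidence of developing stage 1 hypertension and tachycardia, measured by blood pressure and heart rate".

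**Decision rule.** Section 14.0 has two prongs. More than 80% of children randomised to LDX must tolerate the threshold dose for 24 weeks, and the arms must show no statistically significant difference in the incidence of hypertension or tachycardia.

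**Rules that can change exposure before a third reading.**
- Section 12.1, heart rate of 140 bpm or more: an ECG and an assessment, "including the need to reduce or discontinue lisdexamfetamine dose".
- Section 12.1, severe blood pressure with symptoms: "lisdexamfetamine will be discontinued and the participant will be referred to emergent care".
- Section 3.3, intolerance at any time: "the dose will be reduced by 10 mg at weekly intervals until a tolerable dose is achieved".
- Section 17.2: immediate discontinuation after a serious adverse event judged related to study medication or procedures.

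**The ordinary blood pressure sequence (Section 12.1).** After an elevated reading, "blood pressure will be measured again on a separate visit within 2 weeks". Then: "If BP remains elevated on 3 separate visits, the participant will undergo a 24 hour ambulatory blood pressure monitor (ABPM". Only after that: "If hypertension is confirmed, lisdexamfetamine dose will be reduced until blood pressure normalizes". Section 12.1 gives no repeat-visit rule for heart rate.

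**Schedule.** After baseline, blood pressure and heart rate are measured at weeks 4, 8, 12, 16, 20 and 24.

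**The concern.** The outcome counts only elevations that persist over three occasions, while other rules act on the child sooner. If a drug-driven fast heart rate leads to a lower dose and then settles, the third occasion never comes. Section 14.0 does not say how a child with one or two elevated readings is counted after a dose change or at the end of the study. Such a child is a non-case by default.

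Dose reduction is open to both arms, but only in the LDX arm does it remove a drug effect. The misclassification therefore falls mainly on that arm and narrows the difference that the second prong tests. That prong is passed by failing to find a difference, so the error favours proceeding to a larger trial in children.

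Nothing else in the plan corrects this. Follow-up readings after the dose change are real observations, not missing data, so the imputation in Section 14.1 does not apply. Safety review by the DSMB protects the child but does not enter the feasibility rule.

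**Working it through.** The plan states no event rate, event count or power for this comparison, so there is no figure of its own to reproduce.

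**Inputs from the documents.** 44 children randomised 1:1 (Section 1.1), so 44/2 = 22 per arm. Significance at p<0.05 (Section 14.0; two-sided assumed). Six post-baseline vital-sign visits (schedule of events).

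**1. Which children escape both prongs.**
- Tolerability needs more than 0.80 × 22 = 17.6, so 18 children (18/22 = 81.8%; 17/22 = 77.3% fails). A child taken off drug or put below the threshold counts against proceeding here.
- A child reduced from 60 or 70 mg to 40 mg after a reading of 140 bpm or more, whose rate then normalises, passes tolerability whether the threshold is read as at least 30 mg (Section 4.2 and hypothesis H2) or above 30 mg (feasibility sentence in Section 14.0). The same child is not a tachycardia case.
- A child with late onset who is still on drug at week 24 can also escape both.

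**2. Scheduled readings left, counting the visit of first elevation.**

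| First elevated at week | 4 | 8 | 12 | 16 | 20 | 24 |
|---|---|---|---|---|---|---|
| Readings left | 6 | 5 | 4 | 3 | 2 | 1 |

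If occasions mean visits, tachycardia first seen at week 20 or 24 cannot reach three at scheduled visits. Blood pressure first elevated at week 20 still can, using two-week repeats (weeks 20, 22, 24), though ambulatory confirmation on drug is tight. Blood pressure first elevated at week 24 cannot be confirmed on drug.

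**3. Illustration for earlier onset.** Assume no dose change and an independent chance q of an elevated reading at each later visit. Given one elevated reading and n readings left, the chance of reaching three is P(Bin(n−1, q) ≥ 2). At q=0.5:
- week 4: 26/32 = 81%
- week 8: 11/16 = 69%
- week 12: 4/8 = 50%
- week 16: 1/4 = 25%
- weeks 20 and 24: 0%

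Week 12 is the first reading at the planned top dose. There the range is 3(0.3²)(0.7) + 0.3³ = 22% at q=0.3 to 3(0.7²)(0.3) + 0.7³ = 78% at q=0.7. The documents do not give q.

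**4. How many uncounted cases matter.** With no placebo events, two-sided Fisher p = 2·C(22,a)/C(44,a):
- a=5: 2 × 26,334/1,086,008 = 0.0485, significant
- a=4: 2 × 7,315/135,751 = 0.108, not significant

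Section 14.0 says p-values will use robust variance and names no test for incidence. An unpooled Wald test gives:
- 4 vs 0: difference 0.182, SE √(0.182 × 0.818/22) = 0.082, p=0.027
- 3 vs 0: p=0.062

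Under either method, one uncounted LDX case at the boundary turns a stop into a go.

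**5. Illustrative effect on the incidence prong.** Chance of a significant Fisher result with a placebo rate of 0%; all rates are assumed.

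| True LDX rate | All counted | One third uncounted | Half uncounted |
|---|---|---|---|
| 20% | 46% | 16% | 6% |
| 30% | 84% | 46% | 23% |
| 40% | 97% | 74% | 46% |

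**6. Extreme case, also assumed.** Five LDX children reduced to 40 mg for heart rate, all of whom normalise, are recorded as 0 vs 0 events and 22/22 tolerating. Counted as events, they give 5 vs 0 and p=0.0485.

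**The case against.** The strongest reply has four parts.

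- **Hypertension is largely protected.** A reader might infer that both outcomes are equally exposed. They are not: ordinary dose reduction comes after three visits and ambulatory confirmation, and escalation halts only after two additional confirmations. The blood pressure loss is confined to the stop for a severe symptomatic reading, other early reductions or stops (intolerance, a related serious adverse event), and elevation first seen at week 24. This stands.
- **Stopped children do not vanish.** A reader might infer that any child taken off drug becomes a success in the decision rule. Such a child fails the tolerability prong, and five of them (17/22) already block a go decision. This stands.
- **The heart rate action is discretionary.** At 140 bpm or more Section 12.1 requires an ECG and an assessment, not a reduction. No rule specific to heart rate acts between 120 and 139 bpm, and nothing shows that a child without symptoms in that range would be reduced as intolerant. This limits how often the problem arises, but does not remove it.
- **Occasion is undefined for heart rate.** Section 7.2 places three separate occasions at the screening or baseline visit, which may allow several within one visit. On that reading the week 20 and 24 loss largely disappears. The ambiguity itself needs resolving.

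One can also defend counting only sustained elevation under flexible dosing. As a descriptive outcome it is reasonable. As the sole incidence measure in a rule passed by non-significance, it leaves treatment-dependent loss uncorrected.

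**Conclusion.** The point holds in a limited form and should be addressed. It is clearest for tachycardia: no repeat-visit rule, possible dose action after one or two readings, and no counting rule for children reduced but still above 30 mg or first elevated at week 20 or 24. For hypertension it is a smaller gap.

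The direction is known: the loss falls mainly on LDX and favours finding no difference. The size is not, because the documents give no event rates and no rate of heart-rate-driven reductions. What can be said without assumed rates is that one uncounted case can reverse the second prong at 22 per arm. This takes a two-sided test and no placebo events. The late-onset part also assumes that occasions mean visits.

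A reader might go further and conclude that Aim 2 cannot tell whether LDX raises blood pressure or heart rate. The documents do not support that. Both are measured at six post-baseline visits in each arm, outcomes are captured whatever the tolerability, and adverse events are reported. The defect is in the counting rule for the feasibility decision.

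**What to change.** Change the analysis only; no clinical rule needs to change for this. In Section 14.0, Aim 2:

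1. Define *occasion* for heart rate and blood pressure, and reconcile the wording and thresholds in Sections 4.2, 7.2, 12.1 and 14.0. Some differences between strict and non-strict inequalities may come from underlining lost in the PDF text.
2. Keep the three-occasion outcome as one component. In the feasibility comparison, also count as an event any dose reduction or discontinuation made because of blood pressure or heart rate.
3. Report by arm every child with any single elevated reading.
4. Label heart rate first elevated at week 20 or 24, and blood pressure first elevated at week 24, as elevated, unconfirmed, rather than as a non-case.

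**Cost.** New wording in Section 14.0 and one case report form field for the reason for a dose change. The adverse event items listed in Section 17.2 do not include it. The event count may rise in both arms, the added component depends partly on clinical judgement, and the feasibility criterion becomes somewhat harder to meet.
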